$Y_{ijk} = \mu_i + \beta_c C_{ij0} + \gamma_t T_k + (\gamma_c + \gamma_{cf} F_i)(C_{ijk} - C_{ij0}) + \varepsilon_{ijk}$, where the overall treatment effect $\gamma_c + \gamma_{cf} F_i$ is allowed to depend on an indicator F_i of sex. For continuous variables, baseline levels will replace the indicator of sex. Continuous moderator analyses will be refined entering and, adjusting for changes in moderators over time by including baseline and longitudinal levels in the model as

$Y_{ijk} = \mu_i + \beta_c C_{ij0} + \beta_q Q_{ij0} + \gamma_t T_k + (\gamma_c + \gamma_{cq} Q_{ij0})(C_{ijk} - C_{ij0}) + \gamma_q (Q_{ijk} - Q_{ij0}) + \varepsilon_{ijk}$. Here, the overall treatment effect $\gamma_c + \gamma_{cq} Q_{ij0}$ is allowed to depend on baseline levels, and the term $\gamma_q (Q_{ijk} - Q_{ij0})$ adjusts for changes from baseline in the within-subjects sub-model.

Aim 6: Explore the effects of cortisol on resting state regional functional connectivity, and whole brain connectomics.

As discussed in the primary aim, the treatment effects on resting state functional connectivity will be assessed using a randomized regression in a traditional longitudinal cast. The key indices of interest will be overall measures of network integrity (e.g., degree, centrality, rich club architecture, etc.).

Aim 7: Explore the impact of depressive symptoms on memory and hippocampal structure, activation, connectivity and 1HMRS outcomes in response to hydrocortisone administration. Depression as a moderator will be assessed similarly to the moderators proposed in aim 5. However, a dichotomous indicator variable representing baseline group assignment (depressed vs. healthy control) will also be included in the model.

Sample size determination:

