Aims 1, 2, 3, 4 and 6: Complete data from 168 (84 subjects per group) will provide 90% power to detect a treatment effect on hippocampal activation of magnitude 0.08 or greater (correspondingly, $d \geq 0.34$), based on the findings of Brown et al. (2013).³⁴ The magnitude of the treatment effect observed by Brown et al. (2013)³⁴ was 0.16. This is a very conservative estimate because we anticipate enrolling 188 (94 per group) expecting no more than 10% attrition. If attrition rates are abnormally high, at approximately 20%, the completer sample of 150 (75 per group) would provide 80% power and provide sufficient power to detect a statistical difference with an effect size of $d = 0.34$. Complete data from 168 (84 per group) subjects will provide 90% power to detect a treatment effect on hippocampal volume of magnitude 0.06 mm³ or greater, based on the findings of Brown et al. (2015)⁴³ and to detect a treatment effect on declarative memory of magnitude 3.31 or greater, based on the findings of Brown et al. (2013).³⁴ The magnitude of the treatment effect on hippocampal volume observed by Brown et al. (2015)⁴³ was 0.12 mm³, and the magnitude of the treatment effect on declarative memory observed by Brown et al. (2013)³⁴ was 4.25. To power the study for the spectroscopy aims, we used data from a study of patients receiving prednisone for medical illnesses vs. disease matched controls.³⁰ The participants were receiving corticosteroids for a longer duration than in the proposed study, but no studies examining more acute exposure were available. Based on the NAA/Cr values reported we expect a medium effect size ($\sim d = 0.54$). Assuming we have complete data on more than 68 (34 per group) participants we will have approximately 90% power to detect a significant difference in spectroscopy data. This is a conservative estimate given other effect sizes observed in similar work were much larger ($d = 0.84$) which would only need complete data from 40 subjects (20 per group) to observe 96% power. For clinical aim 4, complete data from 136 (68 per group) subjects will provide 90% power to detect a treatment effect on declarative memory of an effect size of $d = 0.38$ or greater, based on the findings of Brown et al. (2013).³⁴ In the case of high attrition rates ($> 28\%$) we would still have over 90% power to observe a significant effect on memory changes. Although data are not available for a sample size estimate for the exploratory aim of rsFC, a sample size of 168 (84 per group) will provide 80% power for an effect size of $d = 0.30$ which is smaller than effect sizes observed in previous work referenced above.

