
Aims 5 and 7: Complete data from 48 participants (50% women) will provide 90% power to detect treatment moderation by sex of magnitude 0.16 for hippocampal activation, 0.12 mm³ for hippocampal volume, and 6.63 for declarative memory (all corresponding to a medium effect size of $d = 0.68$).⁴³ We will assess treatment moderation in the same way but replacing the indicator of female sex with depressed status. Based on previous studies, a difference in declarative memory performance following CS administration between depressed people and controls has a large effect size ($d = 1.1$).⁵⁴ Using the conservative approach of powering the study for the lowest observed magnitude of $d = 0.34$ allows adequate power ($\geq 90\%$) when assessing effects with higher magnitudes.

References for sample size calculations:

Form A

IRB #	STU 2018-0360
--------------	----------------------

Form A

IRB #	STU 2018-0360
-------	---------------

Assessment Schedule

Instrument	Baseline (Visit 1)	Visit 2	Visit 3	Visit 4	Visit 5
Informed consent	X				
Medical and psychiatric history	X				
Concomitant medication review	X	X	X	X	X
Physical exam	X				
SCID-CV for DSM 5	X				
Quick Inventory of Depressive Symptomatology (QIDS-C)	X	X	X	X	X
Young Mania Rating Scale (YMRS)	X	X	X	X	X
Columbia Suicide Severity Rating Scale (C-SSRS)	X		X		X
Systematic Assessment for Treatment Emergent Event (SAFTEE)	X		X		X
Rey Auditory Verbal Learning Test (RAVLT)	X		X		X
Ruff Light Trail Learning (RULIT)	X		X		X
Volunteer Health Questionnaire	X				
Weekly Questionnaire			X	X	X
Prodromal Questionnaire – Brief Version (PQ-B)	X		X		X
Perceived Stress Scale (PSS-10)	X				
Childhood Trauma Questionnaire (CTQ)	X				
International Physical Activity Questionnaire (IPAQ)	X				
Treatment Impressions Inventory (TII)	X				
Internal Status Scale (ISS)			X		X
Blood work (CBC, CMP, morning cortisol) CMP – 8.5 mL; CBC – 4 mL; Cortisol – 10 mL	X		X		X
Blood work (GCR analysis and epigenetics, 2 x 8.5 mL)	X				
Blood work (progesterone in naturally cycling women) Progesterone – 10 mL			X		X
Blood work (Glucocorticoid)	X		X		X
Vitals	X				

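### The claim of 90% power for treatment moderation with 48 completers omits the doubled standard error of a subgroup comparison; on the plan's own main-effect figures, 48 gives about 34–64%

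*Combined protocol and SAP*

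**What the plan says.** The sample size text in section 4.a has two parts.

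- **Aims 1, 2, 3, 4 and 6 (main effects).** 168 completers "will provide 90% power to detect a treatment effect on hippocampal activation of magnitude 0.08 or greater", given as d = 0.34. With higher attrition, "the completer sample of 150 (75 per group) would provide 80% power" for the same d. The matching magnitudes are 0.06 mm³ for volume and 3.31 for declarative memory.
- **Aims 5 and 7 (moderation).** "Complete data from 48 participants (50% women) will provide 90% power to detect treatment moderation by sex of magnitude 0.16 for hippocampal activation". The other magnitudes are 0.12 mm³ and 6.63, all equated with d = 0.68. For depression, "We will assess treatment moderation in the same way but replacing the indicator of female sex with depressed status". The paragraph ends by saying that powering at d = 0.34 "allows adequate power ($\geq 90\%$) when assessing effects with higher magnitudes".

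The Data analysis plan defines the treatment effect (Aim 1) as the within-subject difference between hydrocortisone and placebo. Under Aim 5, that effect "is allowed to depend on an indicator F_i of sex", so moderation is the coefficient on the product of treatment and the indicator. Alpha, sidedness, the SD of the within-subject difference and the within-subject correlation are not given.

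**The concern.** A test of whether the treatment effect differs between women and men, or between depressed participants and controls, contrasts two means, each from half the sample. It is much less precise than the test of the overall effect in the same people. The plan nevertheless gives moderation under a third of the completers that it gives the main effect (48 against 168), although the moderation effect is only twice as large.

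This is the only statement of sample size and power for moderation by sex, and it is carried over to depressed status. The depressed versus non-depressed contrast is named in the study's purpose. A reader who trusts the figure, or who applies the closing sentence to moderation, could take a null interaction as informative when power for a moderate interaction was low.

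**Working it through.** **Inputs.** From Sample size determination: 168 completers, 0.08, 90%; 150 completers, d = 0.34, 80%; 48 completers (half women), 0.16, 90%. Assumed, because not stated: two-sided alpha 0.05, giving z sums of 1.960 + 1.282 = 3.2415 (90%) and 1.960 + 0.842 = 2.8016 (80%). SD_Δ is the SD of the within-subject difference.

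**Standard errors.** Overall effect: SD_Δ/√N. Difference between two halves: √(SD_Δ²/(N/2) + SD_Δ²/(N/2)) = 2·SD_Δ/√N.

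**Consequence that needs no SD.** The moderation magnitudes are twice the main-effect magnitudes: 0.16/0.08 = 2, 0.12/0.06 = 2, 6.63/3.31 = 2.00, 0.68/0.34 = 2. A doubled effect over a doubled standard error leaves the required N unchanged.

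**Where 48 may come from.** A paired test with 24 pairs and d = 0.68 has power Φ(0.68·√24 − 1.96) = 91.5% (t-test 89.1%). That is close to the stated 90%, but it is a one-group main-effect calculation with d doubled and no comparison of subgroups.

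**Power at 48, with the split.** The unit of d is 0.08/0.34 = 0.16/0.68 = 0.2353. Four readings of SD_Δ:

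- A, from 168 and 90%: 0.08·√168/3.2415 = 0.320
- B, d already on the SD of the difference: 0.235
- C, from 150 and 80%: 0.08·√150/2.8016 = 0.350
- D, 0.235 as single-measurement SD with zero correlation: √2·0.2353 = 0.333

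Power = Φ(0.16·√N/(2·SD_Δ) − 1.96). The table gives the t-test version (N − 2 df); the normal approximation is at most 2 points higher. The last two columns use the normal approximation.

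| Reading | SD_Δ | N = 48 | N = 150 | N = 168 | N for 90% | Smallest d with 90% at 168 |
|---|---|---|---|---|---|---|
| A | 0.320 | 40% | 86% | 90% | 168 | 0.68 |
| B | 0.235 | 64% | 99% | 99% | 91 | 0.50 |
| C | 0.350 | 34% | 80% | 84% | 201 | 0.74 |
| D | 0.333 | 37% | 83% | 87% | 182 | 0.71 |

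Example (A, N = 48): 0.16·6.928/(2·0.320) = 1.733; Φ(1.733 − 1.960) = 41%, or 40% by t. Smallest d = 3.2415·2·SD_Δ/(√N·0.2353).

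**Attempts to rescue 48.**

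- One-sided 0.05: 47% (A, recalibrated) and 76% (B).
- Main-effect figures read per group: SD_Δ = 0.08·√84/3.2415 = 0.226 gives 67%; 0.08·√75/2.8016 = 0.247 gives 59%.
- SD that makes 48 exact: 0.16·√48/(2·3.2415) = 0.171, a within-subject correlation of 1 − (0.171/0.2353)²/2 = 0.74 if 0.235 is the single-measurement SD. Main-effect power at 168 would then be Φ(0.08·√168/0.171 − 1.96) > 99.9%, not 90%.

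**Closing sentence.** For moderation of d = 0.34 (0.08) with 168 completers, power is about 31–37% under A, C and D and about 60% under B.

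**The case against.** Five points can be made for the plan.

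1. *One SD fits the main-effect statements approximately.* With zero correlation (D), 168 completers give 87.6% and 150 give 83.8% for 0.08, close to the rounded 90% and 80%. A and C then come from treating rounded powers as exact. This is fair, and D is probably nearest to what was done. It gives 37% at 48, inside the range.
2. *The meaning of the group counts is unclear.* If the main-effect figures apply per group, about 84 to 101 completers in total would suffice for 90% power on moderation, so 168 is not forced. This stands, and the per-group reading raises power at 48 to as much as 67%. It does not reach 90%.
3. *The 34–64% range is not a bound.* Correct: an SD of 0.171 makes the 48 right taken alone. It is ruled out by conflict with the main-effect paragraph, not by the moderation arithmetic. On a pooled count, the 64% reading also misfits, since it gives 99% rather than 90% for the main effect at 168.
4. *The closing sentence follows d = 1.1 for depression,* where 168 completers give over 99% power. That is a possible reading, but the sentence contains no such limit and sits in the moderation paragraph.
5. *The 48 does not drive enrolment, and Aim 7 is exploratory.* True. This limits the consequence, but the stated power is still wrong.

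**Conclusion.** The statement is wrong as written. No reading of 48 as a total, half women, gives 90% power for moderation and also fits the main-effect figures. Power at 48 is about 34–40% on the SDs implied for pooled completers, 64% with d on the SD of the difference, and at most about 67% on a per-group reading. These figures assume two-sided alpha 0.05, equal halves and a common SD_Δ; an uneven sex split would lower them. The factor of two in the standard error depends only on the equal halves and common SD_Δ, not on the value of SD_Δ.

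The design itself is not undermined. At d = 0.68, evenly split subgroups give about 84–99% power with 168 completers and 80–99% with 150; at d = 1.1, 168 gives over 99%. What fails is the written justification, and the closing sentence if applied to moderation: with 168 completers the 90% limit is about d = 0.50–0.74, not 0.34. This should be fixed, but it does not call for a redesign.

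**What to change.** - Withdraw the statement of 90% power with 48 participants, unless its SD is shown and the main-effect paragraph is restated on the same SD.
- State once, for both paragraphs: the SD of the within-subject difference (or the single-measurement SD and the correlation), alpha, sidedness, and whether the per-group counts refer to diagnostic group or treatment sequence.
- Recompute moderation power for sex and for depressed status with standard error 2·SD_Δ/√N, or SD_Δ·√(1/n₁ + 1/n₂) for the expected split, at 168 and 150 completers. For d = 0.68, expect about 90% and 86% (A), 99% and 99% (B), 84% and 80% (C), or 87% and 83% (D).
- Limit the closing sentence to main effects, and report separately the smallest moderation effect detectable with 90% power.

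The cost is text only. Enrolment, analysis model and visits stay as they are; the stated power for moderation becomes less favourable.

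### The claimed power of at least 90% for depression moderation (exploratory Aim 7) rests on effect sizes that are not on the scale of the moderation test

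*Combined protocol and SAP*

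**What the plan says.** All references are to section 4.a of the combined protocol and SAP.

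- **Data analysis plan, Aims 5 and 7.** The moderation coefficient multiplies the change in assigned condition, so it is a between-group difference in the within-subject treatment effect. Depression is handled like the Aim 5 moderators, except that "a dichotomous indicator variable representing baseline group assignment (depressed vs. healthy control) will also be included in the model". That indicator comes on top of the moderation term.
- **Sample size determination, first paragraph (Aims 1 to 4 and 6).** The main-effect claim reads: "Complete data from 168 (84 subjects per group) will provide 90% power to detect a treatment effect on hippocampal activation". The effect size in question is 0.08, which the plan equates with d = 0.34.
- **Sample size determination, Aims 5 and 7.** With 48 completers, half of them women, the plan claims 90% power for moderation by sex at d = 0.68 (6.63 memory points). It continues: "We will assess treatment moderation in the same way but replacing the indicator of female sex with depressed status". It then reports that "a difference in declarative memory performance following CS administration between depressed people and controls has a large effect size", with d = 1.1. It closes by saying that powering on d = 0.34, the smallest observed effect, "allows adequate power ($\geq 90\%$) when assessing effects with higher magnitudes".

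Alpha, sidedness, the SD that defines d and the within-subject correlation are not stated.

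**The concern.** The only depression-specific effect size in the sample-size text is worded as a group difference in performance after corticosteroid. The Aim 7 model, with its separate group term read as a main effect, takes any constant difference between depressed participants and controls out of the moderation coefficient. An effect size that may contain that difference cannot show that the moderation test is well powered.

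The closing sentence has a related fault. It takes an effect size from the treatment main effect, which uses the whole sample, and extends it to effects that include a contrast between two halves of the sample.

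At stake is how a null Aim 7 memory result is read. Purpose and objectives (section 1) lists a differing effect of hydrocortisone in depressed and non-depressed people among the study's interests. A reader who is told that power is at least 90% may give a null result more weight than the stated inputs justify.

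**Working it through.** **1. What d = 1.1 can say about moderation.** On one outcome scale, the gap after drug equals the gap without drug plus the difference in response:

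1.1 = g + m, so m = 1.1 − g.

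The documents do not give g. If g is 1.1, m is 0. If g is 0, m is 1.1. If the groups differ the other way without drug, m exceeds 1.1. The figure alone does not fix m.

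**2. Formulas.** Let σ be the SD of the hydrocortisone-minus-placebo difference, in the units of d. With N completers split equally between depressed participants and controls, the noncentrality λ is:

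- main effect: λ = d√N / σ
- moderation: λ = d√N / (2σ)

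At the same N and σ, moderation must be twice as large as a main effect to have the same power. Powers below use the noncentral t with N − 2 df. Two-sided alpha 0.05 is an assumption, and so is reading 84 per group as depressed v control.

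**3. The plan's own figures.**

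- Taking d = 1.1 as the moderation effect, 84 v 84 gives at least 99.9% power for within-subject correlations from 0 to 0.75. The arithmetic works if 1.1 is the right quantity.
- If d is in SDs of the within-subject difference (σ = 1), the main-effect statement (d = 0.34, 90%) does not reproduce: 168 completers give 99.2% and a single group of 84 gives 86.9%.
- On the same unit, the sex-moderation statement (48, d = 0.68, 90%) gives 63.5%. It reaches 90.3% if d is in outcome SDs and the correlation is 0.75.

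Since neither statement reproduces directly with σ = 1, I solved each for the σ that it implies.

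**4. The two statements use the same unit.** Activation: 0.08/0.34 = 0.16/0.68 = 0.235. Volume: 0.06/0.34 = 0.12/0.68 = 0.176. Memory: 3.31/0.34 = 9.74 and 6.63/0.68 = 9.75. A change in the unit of d therefore does not explain the disagreement below.

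**5. Basis A, the main-effect statement (168, d = 0.34, 90%).** 90% power at 166 df needs λ = 3.26.

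- σ = 0.34 × √168 / 3.26 = 1.35
- moderation at N = 168: λ = d × 12.96 / (2 × 1.35) = 4.79d
- 90% power: d = 3.26 / 4.79 = 0.68, about 6.6 memory points
- at d = 0.34: λ = 1.63, power about 37%

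**6. Basis B, the moderation statement (48, d = 0.68, 90%).** 90% power at 46 df needs λ = 3.31.

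- σ = 0.68 × √48 / (2 × 3.31) = 0.71
- moderation at N = 168: λ = d × 12.96 / (2 × 0.71) = 9.11d
- 90% power: d = 3.26 / 9.11 = 0.36, about 3.5 memory points
- at d = 0.34: λ = 3.10, power about 87%

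**7. Cross-check.** Basis A applied to 48 participants at d = 0.68 gives λ = 0.68 × 6.93 / (2 × 1.35) = 1.74, or power of about 40% against the stated 90%. If d is in outcome SDs, σ² = 2(1 − ρ), and the implied correlations are about 0.09 (A) and 0.75 (B).

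| Moderation, 84 v 84 | Basis A | Basis B | σ = 1 |
|---|---|---|---|
| Detectable d at 90% power | 0.68 | 0.36 | 0.50 |
| Power at d = 0.34 | 37% | 87% | 59% |

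**The case against.** **The 90% is not derived from 1.1.** This is correct. The closing sentence attaches it to d = 0.34, so deleting 1.1 alone would not repair the claim. But 0.34 is a main effect, and at that size moderation falls short of 90% on all three bases in the table.

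**The plan already gives a moderation-scale figure.** It does: d = 0.68 with 48 participants, extended to depression. On that basis 168 completers do well, with 98% power at d = 0.436 and 78% at d = 0.30. This stands, and it is why the main-effect calibration cannot be presented as the plan's only variance basis. It does not make 1.1 a moderation effect, and the plan cites no placebo-adjusted depression effect that reaches 0.36 or 0.68.

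**The wording may be shorthand for a difference in response.** Possible. The cited source is not available here, so the sponsor must say which contrast it is.

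**A conflict with Aim 4.** A reader might infer that a true difference in response of 1.1 contradicts the pooled memory effect used for Aim 4. The documents do not support this: the Aim 4 text states the smallest effect detectable with given power and does not predict a pooled effect.

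**The aim is exploratory.** This is true, and it lowers the consequence.

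**Conclusion.** The statement of at least 90% power is unsupported for Aim 7. As worded, d = 1.1 is a contrast after drug that may include a pre-existing gap. It also concerns declarative memory only, whereas Aim 7 also covers hippocampal structure, activation, connectivity and spectroscopy. The d = 0.34 is a main effect.

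The size of the problem depends on which of the plan's two statements supplies the variance. The claim fails for moderation effects between 0.34 and 0.68 on the main-effect basis, but only between 0.34 and about 0.36 on the 48-participant basis. Both ranges assume two-sided alpha 0.05 and 84 depressed v 84 control completers.

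A reader might go further and conclude that Aim 7 is underpowered. The documents do not show that. They do not give the true difference in response, and the more favourable basis leaves good power for moderate differences. What is established is that the stated support does not fit the test, and that the plan's two power statements cannot both hold with one variance. For an exploratory aim this is a modest point, but it corrects a stated figure.

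**What to change.** In section 4.a, Sample size determination, Aims 5 and 7:

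1. Delete d = 1.1 as support for Aim 7. Alternatively, if the cited source reports the depressed-minus-control difference in the corticosteroid-minus-placebo change, put that in its place.
2. Do not apply the main-effect d = 0.34 to moderation.
3. Reconcile the variance behind the 168-completer main-effect statement with that behind the 48-participant moderation statement.
4. Then state the depression-by-drug difference detectable with 168 completers, giving alpha and sidedness, the SD that defines d, the within-subject correlation, and what per group means.

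This costs rewording and one recalculation, with no added participants or procedures. The stated power for an exploratory aim will probably look less favourable.

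### The d = 0.34 labelled as the lowest observed effect is the planned main-effect size, and its 90% power does not carry over to the moderation analyses of Aims 5 and 7

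*Combined protocol and SAP*

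**What the plan says.** Both passages are in the combined protocol and SAP, item 4.a, under "Sample size determination".

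- **Aims 1, 2, 3, 4 and 6.** "Complete data from 168 (84 subjects per group) will provide 90% power" for a "treatment effect on hippocampal activation of magnitude 0.08" or more, with the standardised size given as "correspondingly, $d \geq 0.34". The activation effect in the cited crossover study is reported as 0.16. For volume, the detectable effect is 0.06 mm³ and the observed one 0.12 mm³. For declarative memory they are 3.31 and 4.25.
- **Aims 5 and 7.** With 48 participants, half of them women, 90% power is claimed for moderation by sex of 0.16 (activation), 0.12 mm³ (volume) and 6.63 (memory), "all corresponding to a medium effect size of $d = 0.68". Depression status is to be handled in the same way, and a depressed-versus-control memory effect of d = 1.1 is cited. The paragraph then says that "powering the study for the lowest observed magnitude of $d = 0.34" gives at least 90% power "when assessing effects with higher magnitudes".

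Alpha, sidedness, the SD that defines d and the within-person correlation are not stated.

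**The concern.** Two things look wrong in the closing sentence. First, it describes 0.34 as an observed effect, whereas the preceding paragraph presents it as the effect the study was sized to detect. Second, it ends the paragraph that justifies the moderation aims, so a reader will take its 90% as covering them. The 90% at 0.34 was derived for the overall treatment effect. A difference between two subgroup effects is estimated less precisely from the same participants.

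Aim 5 lists many moderators, and a planning effect is given only for sex. Aim 7 concerns depression status, a stated interest of the study. If the sentence stands, a null moderation result could be cited as coming from an analysis with 90% power when, for effects not far above 0.34, it did not.

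**Working it through.** **Is 0.34 an observed effect?** The implied SD for activation is 0.08/0.34 = 0.235, and 0.16/0.68 = 0.235, so both paragraphs use one scale. The observed effects on that scale are:

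- activation: 0.34 × 0.16/0.08 = 0.68
- volume: 0.34 × 0.12/0.06 = 0.68
- memory: 0.34 × 4.25/3.31 = 0.44

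The other effects drawn from earlier work are 0.54, 0.84 and 1.1. None is 0.34.

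**Can the plan's power figures be reproduced?** Two-sided alpha 0.05 is assumed, with normal approximations unless noted.

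| Stated | Two-sample, n per group | Noncentrality d√(n per group) | All completers as one paired sample |
|---|---|---|---|
| 84 per group, d = 0.34: 90% | 59.6% | 87.6% | 99.3% |
| 75 per group, d = 0.34: 80% | 54.9% | 83.8% | 98.6% |
| 24 per group, d = 0.68: 90% | 65.4% | 91.5% | 99.7% |

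No single convention returns all three. The middle one comes closest and matches the moderation figure. I therefore computed moderation power under three readings, for 168 completers split 84/84. The noncentrality for 90% power is 1.960 + 1.282 = 3.24.

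1. **Main-effect anchor** (168, d = 0.34, 90%). In a balanced split, the difference between two half-sample effects has twice the standard error of the overall effect. The noncentrality at d = 0.34 is 3.24/2 = 1.62, and power is Φ(1.62 − 1.96) = 36.7%.
2. **d in SDs of the within-person difference.** The noncentrality is 0.34 × √(84/2) = 2.20, and power is 59.6% (59.1% by noncentral t).
3. **Scaled from the plan's moderation figure** (48, d = 0.68, 90%). The noncentrality is 3.24 × (0.34/0.68) × √(168/48) = 3.03, and power is 85.8%.

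| Moderation d | Reading 1 | Reading 2 | Reading 3 |
|---|---|---|---|
| 0.34 | 36.7% | 59.6% | 85.8% |
| 0.40 | 47.9% | 73.6% | 94.6% |
| 0.50 | 66.4% | 90.0% | 99.4% |
| 0.68 | 90.0% | 99.3% | >99.9% |
| Smallest d with 90% | 0.68 | 0.50 | 0.36 |

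The smallest d values are 2 × 0.34 = 0.68, 3.24/√42 = 0.50 and 0.68 × √(48/168) = 0.36. At d = 1.1 every reading gives at least 99.9%. If all 188 enrolled completed, power at d = 0.34 would be 40%, 65% and 89%.

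If 84 per group means that each of the depressed and control groups alone has 90% power, the standard error of their difference is √2 times that of one group. The noncentrality is then 3.24/√2 = 2.29, and power at 0.34 is 63%.

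**Do the two anchors agree?** If 168 completers give 90% for a main effect of 0.08, they also give 90% for moderation of 0.16, which is twice the effect with twice the standard error. With 48 participants the noncentrality falls to 3.24/√(168/48) = 1.73, and power is 41%, not 90%. Conversely, if 48 give 90% for moderation of 0.16, then 168 have a noncentrality of 3.24 × 1.87 = 6.06 for a main effect of 0.08. That is power above 99.9%, not 90%.

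**The case against.** The strongest defence is that the plan states a moderation figure of its own. Scaled to 168 completers, it gives about 86% at 0.34 and passes 90% from about 0.36, so the overstatement nearly vanishes. This stands to the extent that 37% to 59% is not the only range the documents allow. It does not rescue the sentence, because that figure is incompatible with the stated main-effect power, and the documents do not say which is right.

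A second defence is that d may use the single-occasion SD with a high within-person correlation r. The moderation noncentrality is then d√84/(2√(1 − r)), giving about 87% at r = 0.75 and 93% at r = 0.8 for d = 0.34. No correlation is stated, however. At r = 0.8 the main-effect noncentrality would be 0.34 × √168/√0.4 = 6.97, which again contradicts the stated 90%.

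Third, the sentence follows directly on effects of 0.68 and 1.1, and both reach 90% at 168 completers. That stands and limits the point to smaller effects. Aim 7 is also labelled exploratory, and the plan sets no rule for interpreting null moderation results, so misreading them is a risk and not a certainty.

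A reader might infer that the doubled sizes (0.16, 0.12, 6.63) themselves show the doubled standard error of a moderation contrast. They do not: they are quoted for 48 participants and the undoubled ones for 168, and √(168/48) = 1.87 accounts for nearly all of the doubling.

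**Conclusion.** Wrong as written, on two counts. The value 0.34 is the planned detectable main effect, half the observed activation and volume effects. And at least 90% power above 0.34 does not carry over to moderation. At d = 0.34 and 168 completers, power is about 37%, 59% or 86% under the three readings, with 90% reached at about 0.68, 0.50 or 0.36. The stated power figures for 168 and 48 participants cannot both hold.

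This rests on two-sided alpha 0.05, an even split and equal variability in the two subgroups. One-sided testing would raise the first two figures to about 43% and 71%.

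A reader might infer that Aims 5 and 7 are underpowered for the effects they were planned around, or that the label makes the trial too small. The documents support neither. The named effects reach 90% at 168 completers, and 0.34 lies below every effect reported as observed, so the label errs cautiously. Nor can one say that 0.34 was never observed anywhere: the cited sources are not available here, and the point is only that no observed effect reported in the documents equals it.

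**What to change.** In the sample-size text:

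- Describe 0.34 as the planned main-effect size, half the observed activation and volume effects.
- Limit the claim of at least 90% power above 0.34 to main effects.
- State alpha, sidedness, the SD behind d, the within-person correlation, and whether group means treatment sequence or depression status.
- Correct the 48-participant figure or reconcile it with the main-effect figure. Adding a new moderation value beside it unchanged would create a further contradiction.
- State separately the moderation effect detectable with 90% power at 168 completers: about d = 0.68 on the main-effect anchor, or about 0.50 if d uses the SD of within-person differences. If the 48-participant figure proves to be the sound one, the value is about 0.36 and the main-effect power must be restated instead.

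No design, sample-size or analysis change is needed. On the first two bases, the cost is a less favourable stated power for Aims 5 and 7.
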